Attachment D Investigator Agreement Attachment E Financial Disclosure

#### 1.0 INTRODUCTION AND BACKGROUND

Barrett's Esophagus (BE) is a premalignant lesion which can lead to esophageal adenocarcinoma. This particular cancer is one of the most rapidly increasing and deadliest cancers in the United States. Patients with BE are up to 40 times more at risk of adenocarcinoma than individuals without BE.

Once diagnosed with BE, a patient enters a life-long surveillance program in which upper endoscopy (Esophagogastroduodenoscopy or EGD) with biopsy are performed to survey the progression of the Barrett's tissue to cancer. For more than 20 years, many technologies have been evaluated for ablation of BE. Elimination of BE and restoration of squamous esophageal lining has been demonstrated through ablation; however, no ablation technology currently provides the necessary attributes for wide-spread adoption into a community setting. Current BE technologies such as Radio Frequency Ablation (RFA) suffer from 'usability' drawbacks such as the need for precise sizing, multiple deployment steps, intensive training for the physician and large controller units. Even with these limitations, the market for these technologies is growing at a rate of 60% annually and has become the standard of care for certain BE patients.

Similarly, patients with dysplasia developing in the squamous-lined esophagus are at risk for developing esophageal squamous cell carcinoma (SCC). In the West, these patients often have a history of smoking, alcohol, or rare associated risk factors. In the East, SCC is more common than adenocarcinoma arising in BE. Hence, the potential worldwide clinical impact of a safe and effective esophageal ablation system for precancerous neoplasia is an important consideration for further testing and development of this novel therapy.

Cryoablation has been shown to cause cell death through two distinct mechanisms. The first is ice formation in the extracellular fluid matrix. This causes cells in that matrix to eject pure water which raises the salinity content of the cell which provides protection against intracellular ice formation by decreasing the freezing point of the cell. This action will induce apoptosis in some percentage of the cells is due to dehydration of the cell. Generally, apoptosis (i.e., programmed) occurs at freezing temperatures warmer than  $-15^{\circ}$ C under controlled cooling rates. The second mechanism is ice formation within a cell. This will typically cause necrosis of the cell due to mechanical destruction of the cell wall caused by ice crystals.

Apoptosis is the typical mechanism for cell death. Apoptotic cell death does not induce a systemic healing response as the contents of the cell are coated with a membrane and are absorbed locally. Necrosis of the cell occurs when the cell wall is ruptured. The body interprets this as injury and acts appropriately to repair the area. Because of the body's response the cell necrosis and the desire for replacement of normal esophageal tissue, C2 believes this is the appropriate mechanism to ablate Barrett's Esophagus.

The CryoBalloon Focal Ablation System (CbFAS) is designed to address many of the limitations of ablation technologies that have been listed. The System has three main components – the delivery catheter with balloon probe, a handle, and a small cylinder containing the cryogenic fluid. There is no capital equipment involved – the system is completely single-patient use. The system utilizes one balloon probe for all sizes of esophagi. Access for treatment is simplified as the system utilizes the working channel of the endoscope.

The simplicity of the System allows for many potential benefits to the patient, the physician, and hospital. Some of the benefits may include a shorter and safer procedure, an easier deployment minimizing the need for anesthesiology, and smaller inventory requirements and no capital equipment improving capital resource utilization

NOTE: Please refer to the Investigator's Brochure for more extensive background information and literature search results.

PROTOCOL# CP-0007/ Version: 8 29April 2019

#### PRELIMINARY EXPERIENCE AND DATA

The System has undergone acute and chronic animal testing. The testing was conducted to study the safety, deliverability and performance characteristics of the System. The studies were conducted for the evaluation of the device in a normal pig esophagus at dimensions very similar to a human esophagus. General follow-up time frames were either 4 days or 28 days. A summary of prior pre-clinical testing performed on the System is provided in the Investigator's Brochure. A summary of the animal data is also included in the Appendix below.

A clinical trial has been conducted to study the safety and performance characteristics of a full-circumferential version of the CryoBalloon Ablation System. The Investigator's Brochure highlights the differences between the two devices with the major difference being that the Focal System ablates a far smaller area. Data has been presented at the DDW 2012. The abstract for the study is included in the Investigator's Brochure with final results not yet published. Preliminary results show the full-circumferential system is safe and has good efficacy on the ablation of esophageal mucosa.

The CbFAS device has been cleared by the U.S. Food and Drug Administration under K101825. The device will be used in accordance with the manufacturer's labeling under this protocol.

The international single arm CbFAS trial conducted under the original protocol for this study has been completed and the manuscript submitted to Endoscopy journal for publication. See more detail on the preliminary results in separate attachment submitted. In this multicenter, prospective non-randomized trial 39 patients were treated, each subject receiving 1-2 ablations of 6, 8 or 10 seconds. Symptoms were assessed directly and 2 days post-cryoablation. Follow-up endoscopy was performed after 6-8 weeks to assess the ablation response. Outcome parameters were incidence of adverse events, pain, esophageal stricture formation, and ablation response by cryogen dose. *Results*: 56 ablations (10 with 6-sec, 28 with 8-sec, 18 with 10-sec) were performed. Six ablations failed due to device malfunction (n=3) or other reasons (n=3). Median (IQR) procedure time was 7 min (4-10) min. No major adverse events occurred; six patients had a minor mucosal laceration requiring no intervention. Mild pain was reported in 27% of patients immediately after cryoablation and in 14% after 2 days. After 6-8 weeks no strictures had developed. Full squamous regeneration was seen in 6 [60%] of 6s-areas; 23 [82%] of 8s-areas, 100% of 10s-areas). These study results suggest that focal cryoablation of BE with the newly developed CbFAS is feasible, safe, and results in squamous regeneration in the majority of patients. These results were recently published (Scholvinck et al, Endoscopy July 2015 – paper uploaded into eIRB separately)

Furthermore, [name] has treated 41 BE patients and 10 patients with esophageal squamous low grade and high grade dysplasia (neoplasia) within this study and more treated within the clinical cryotherapy program at Johns Hopkins Hospital) with successful ablation in 1-3 outpatient procedures using multifocal cryoballoon ablations, in keeping with standard of care treatment approach to ablation. Research and clinical patients have tolerated cryoablation well, with visible treatment response.

Based upon the results of 2 clinical trials completed under this IRB-approved study,

[name] plans to continue this single center (industry sponsored) study to continue the evaluation of safety, effectiveness and 5-year durability of cryoballoon ablation for esophageal neoplasia.

### 2.0 SUMMMARY DEVICE DESCRIPTION AND USE

[figure not shown]
The System has three main components – the delivery catheter with balloon probe, a handle, and a small cylinder containing the cryogenic fluid. Deployed through the working channel of an endoscope, the operation of the System is very similar to the deployment of dilatation balloons. The balloon is made of a conformable material. Once deployed, the balloon is simultaneously inflated and cooled with cryogenic fluid delivered from the handle. Due to the conformability of the balloon material, no sizing procedure is required. Additionally, one balloon can ablate a full range of esophagi (approximately 20mm to 32mm in diameter). Esophageal cells are ablated as the balloon comes into contact with the esophagus for less than 15 seconds. After ablation, the System is repositioned for additional ablation or withdrawn.

Cryoballoon ablation system includes

- CryoBalloon Focal Ablation Catheter (FG-1009) Sterile single-patient use with a balloon at end of Catheter
- CryoBalloon Focal Ablation Handle (FG-1012) Single-patient use and battery-powered
- CryoBalloon Ablation Cartridge (FG-1010) Nitrous oxide, single-patient use
- Sidecar External Working Channel (FG-1011)- Single-patient use

Proposed System Benefits include the following:

- Completely Disposable System
  - No investment in equipment
  - No service, maintenance or set-up of equipment
  - No special storage requirements

- Minimize disposable devices necessary for procedure
- Lower inventory costs

- Shorter procedure times
- o Improve resource utilization
- · Working channel access of system
  - Less discomfort to patients

Potential move from than general or heavy sedation to conscious sedation

Latest device improvements:

#### Principle of pre-inflation and self-sizing

The balloon pre-inflates and contacts the esophagus wall prior to the actual ablation. Pre-inflating the balloon against the esophagus creates an intimate contact with the esophagus and enables the user to visualize and identify targeted ablation areas through the inflated balloon.

The self-sizing feature of the balloon allows inflation to a range of esophageal diameters without applying pressures beyond ~6 psi. Concurrently, the inflation does not exceed beyond the esophagus inner diameter. The self-sizing balloon concept is also similar to the Barrx™ Halo 360 Sizing Balloon, where it uses a 33.7mm non-compliant balloon and inflates it to over 4 psi in the esophagus to estimate the esophagus diameter.

### **Description of change**

The system is composed of a catheter, a handle, and nitrous oxide cartridges – nitrous oxide is the cryogenic fluid used to ablate unwanted tissue. The design of the catheter and the cartridge remain the same. The handle design has been improved to reduce the pre-inflation pressure within the balloon from ~6 psi to ~3 psi for a 50% decrease. Pressures during ablation are ~3 psi.

[figure not shown]
The mechanism in the handle that controls the nitrous oxide exhaust gas has been modified from a mechanical valve to an electro-mechanical valve (solenoid). Due to the solenoid valve change, balloon pressure during pre-inflation and ablation can be more accurately controlled and decreased by the mentioned 50%.

### **Purpose of Change**

The principle of operation of the C2 ablation system is to inflate the ablation balloon against the esophagus wall. The self-sizing capability of the system is enabled by the low operating pressure within the balloon. The pre-inflation pressure may reach ~6psi, while the pressure during ablation is ~3psi; therefore, it is desirable to lower the pre-inflation balloon pressure be similar to the ablation pressure, which also minimizes potential damage to the esophagus. A pressure reduction of approximately 50% is benefitted by the handle design change. An operating pressure of ~3 psi during pre-inflation and ablation is also lower than the 4+ psi, or approximately 25% lower than the Barrx™ Halo 360 Sizing Balloon procedure.

All procedures will be performed in the outpatient endoscopy unit by using monitored anesthesia care or conscious sedation, per standard institutional practice. The physician will perform an upper endoscopy using an endoscope with a therapeutic channel to accommodate the CbFAS balloon and to verify the treatment zone in the esophagus. Alternatively, a commercially available 510k-FDA approved accessory tube called the "sidecar", can be attached to a standard non-therapeutic channel upper endoscope (more commonly available in endoscopy units compared to a therapeutic endoscope) and the cryoballoon advanced through the "sidecar" as shown in the images below.

PROTOCOL# CP-0007/ Version: 8 29April 2019 **CONFIDENTIAL** 

This document contains proprietary and confidential information of C2Therapeutics, Inc. Do not copy, distribute, or share with others without prior written authorization from C2 Therapeutics, Inc.

The System is deployed under direct visualization.

Refer to the Instructions for Use (IFU) for specific device use instructions.

### 3.0 CLINICAL INVESTIGATIONAL PLAN (CIP)

### 3.1 CIP Summary

Title: Evaluation of CryoBalloon Focal Ablation System on Human Esophageal

Epithelium..

Name of Device: Pentax C2 CryoBalloon Focal Ablation System (System) –

The System is intended to be used as a cryosurgical tool for the destruction of

unwanted tissue, specifically for endoscopic applications.

**Indications for Use:** 

**Study Purpose:** 

Under this protocol, Cryoballoon ablation will be performed on patients with Barrett's Esophagus (BE) and localized esophageal squamous neoplasia.

Patient Population:

Patients who have Barrett's Esophagus and esophageal squamous neoplasia

and meet the protocol entry criteria.

The purpose of this study is to assess the safety, feasibility and performance

of the C2 Focal Cryoablation System in patients with BE and esophageal

squamous neoplasia.

This study is:

Study Design: • Prospective

Single center (Johns Hopkins Hospital)

Non-randomized

Sample Size: It is estimated that up to 100 patients will be enrolled under this protocol.

**Number of Sites:** 

**Study Procedures:** 

One institution: Johns Hopkins Hospital

The study will involve100 subjects with each subject receiving up to 24 ablations (multifocal) using the C2 System Focal Ablation System per treatment session. Ablations will be at 5, 6, 8, 10 or 12 seconds. Up to 5 treatment sessions 8-12 weeks apart within 12 months may be performed, if there is residual BE or abnormal squamous mucosa, until all disease is eliminated, by endoscopic biopsy. The ablations will be performed in an area of BE that is > 1cm 2 or recurrent BE at the gastroesophageal junction (GEJ).

Prior and intervening endoscopic mucosal resection (EMR) may be performed

for esophageal lesions, as part of standard care.

After completing cryoablation treatment, subjects return for EGD with

surveillance biopsy at every 2-3 months for first year and every 6 months for the second year as part of standard care then annually for next 3 years for

PROTOCOL# CP-0007/ Version: 8 29April 2019

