#### **Primary Endpoints**

- Device Performance
- Adverse events
- Efficacy for complete elimination (CE) of all esophageal dysplasia
- Efficacy for complete elimination of all BE

All adverse events

Esophageal stricture formation and assessment of clinical dysphagia.

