**CONFIDENTIAL** 

ablation performed inside the identified area of BE. The use of CryoBalloon Focal Ablation System is in conformance to the IFU.

- 11. Document the location of the top and bottom of the ablation zone (insertion depth of the endoscope and orientation in the endoscopic field). This is done by videorecording, photo documentation and/or by recording the localization (of the ablated area). Placing a tattoo at the top of the ablation zone is optional to further identify the exact location of the ablation zone. Document the location of the tattoo (insertion depth of the endoscope and orientation in the endoscopic field).
- 12. Up to 5 outpatient ablation endoscopic procedures can be performed 8-12 weeks apart per patient (up to 24 per procedure) to achieve complete ablation of dysplasia. This treatment schedule is comparable to that for other standard endoscopic ablative techniques, such as radiofrequency ablation and carbon dioxide cryotherapy

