# 3.5.5 Stages 5 and 6 –12 24, 36, 48, 60 Month Assessments

1. As part of standard care, treated patients will be monitored by outpatient upper endoscopic procedures after completion of cryoballoon ablation (Stage 2), with EGDs every 3 months for first year (stage 5), then every 6 months for the second year to month 24 (stage 6). The endoscopic findings (detailed above) and pathology results will be documented at month 12,24, 36, 48 and 60 months for study endpoint analyses.

PROTOCOL# CP-0007/ Version: 8 29April 2019 CONFIDENTIAL 15 of 33

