#### Table 2 - Schedule of Treatments and Assessments

\*Adverse events occurring prior to the procedure will be documented in the patient's medical record but will not count as related to the investigational device or procedure.

\*Treatments: Baseline or initial treatment visit = visit 0; subsequent treatments: 2nd to 5th treatment visits (10 weeks), as needed, up to 12 months from baseline. Treatments only if there is visible residual disease; no endoscopically- visible BE or abnormal squamous mucosa, biopsy will be performed using standardized protocol, beginning at the gastric cardia then the neo-Z line and every 1-2 cm proximal, to sample the previously treated BE areas (according to current standard of care).

Subjects can opt-out of participating in the surveillance phase of the trial after 12 months, if local endoscopic surveillance is preferred.

Adverse events: any patient with pain, dysphagia, fever, or other non-serious adverse event will be called weekly from day 8 to 1 month post-treatment or until AE resolution. Adverse events will be graded and recorded according to standard NIH definitions.

STUDY STAGES $\rightarrow$	Stage 1	Stage 2		Stage 3		Stage 4	Stage 5	Stage 6	
Assessments	Informed Consent/ Baseline Evaluation	Initial Treatment *	Immediately Post-/prior to discharge (up to 12 hours)	1-day Phone Contact (±1 day)	7-day Phone Contact (+/- 1 day)	30-day Phone Contact (+/- 1 day	EGD for treatment or biopsy ( q 8-12 weeks)	EGD for biopsy (endpoint assessment) (12 months)	EGD (24, 36, 48 and 60 months)
Consent	X								
Review of Medical History	x								
Review of Medications	Х	Х	X	Х	Х	Х	X		
Review of General Health	x	х	X	Х	X	X	x		
Physical Exam	X								
Pain and dysphagia Assessment		х	X	X	X	X	x	X	

PROTOCOL# CP-0007/ Version: 8 29April 2019

CONFIDENTIAL

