# 3.7 Study Withdrawal

Subjects may be terminated or withdrawn from the study for the following reasons:

- Subject death.
- Voluntary withdrawal meaning that subject voluntarily chooses not to further participate in the study.
- Loss to follow-up meaning that the subject is or does not return for further follow up.

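### The plan does not say how patients with residual disease at the 5-session/12-month limit are scored at months 24 to 60, so long-term complete elimination could be overstated

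*Combined protocol and SAP*

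**What the plan says.** - **Treatment limit.** Section 3.1, Study Procedures: "Up to 5 treatment sessions 8-12 weeks apart within 12 months may be performed". The notes to Table 2 repeat the limit as "up to 12 months from baseline". Sessions continue while disease remains and end once it is gone. No text covers the patient who reaches the limit with disease still present.
- **Endpoints.** Two of the primary endpoints in 3.1 are "Efficacy for complete elimination (CE) of all esophageal dysplasia" and "Efficacy for complete elimination of all BE". Neither has a time point, a link to study treatment or a failure rule.
- **Who is read out, and when.** Section 3.5.5 follows treated patients, not only those who cleared, and says "pathology results will be documented at month 12,24, 36, 48 and 60 months for study endpoint analyses".
- **Leaving the study.** Section 3.7 begins "Subjects may be terminated or withdrawn from the study for the following reasons" and lists death, voluntary withdrawal and loss to follow-up. Treatment failure is not listed. The notes to Table 2 also let any subject opt out of surveillance after 12 months in favour of local follow-up.
- **Analysis.** Section 7.2 tabulates binary outcomes with exact binomial intervals and compares them with historical data. Section 7.4 leaves missing values out and rules out imputation.
- **Recording.** Table 2 has no row for non-study ablation, resection or surgery.

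**The concern.** A patient uncleared at the limit is one in whom the study regimen has not worked. Two things could then happen.

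First, the patient could be treated elsewhere. The documents show that other treatment is within reach. The background section reports patients "more treated within the clinical cryotherapy program at Johns Hopkins Hospital", and 3.5.2 step 12 refers to "other standard endoscopic ablative techniques, such as radiofrequency ablation and carbon dioxide cryotherapy". If such treatment clears the disease, the next biopsy is negative, and a plain tabulation has no reason to call it anything but CE.

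Second, the patient could opt out of surveillance. The later results are then missing, 7.4 leaves them out, and a known failure disappears from the denominator.

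The long-term result is what is at stake. Section 3.2 names long-term effectiveness as an aim, and the background section names 5-year durability. A CE rate could rise after month 12 with no study treatment given, and 7.2 would carry it into the historical comparison. If non-study treatment is not recorded, the affected patients may be hard to identify afterwards.

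**Working it through.** **There is no stated figure to reproduce.** The sample size of up to 100 has no hypothesis, power or precision target behind it. The check asks what the written rules do to a known failure.

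**Inputs**
- N = 100 (3.1). This is a round illustration. Each CE endpoint applies only to patients who had that condition at baseline, so the real denominators will be smaller.
- F = share uncleared at the limit. Not in the documents; shown at 10%, 20% and 30%.
- c = share of those later cleared outside the study; m = share of those later missing. Not in the documents; each can run from 0 to 100%, with c + m at most 100%.
- All other patients are assumed to stay clear and to be observed.
- Intervals are exact binomial, as in 7.2. The plan gives no level, so 95% is assumed.

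**Formulas**
- Uncleared patients scored as failures: CE = 1 − F.
- As observed, with missing values left out: CE = (1 − F + F·c) / (1 − F·m).

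The second expression is never below the first, because F·c adds to the numerator and F·m shrinks the denominator. They are equal when c = m = 0. With m = 0 the shift is exactly F × c. With c = 0 it is (1 − F)·F·m / (1 − F·m), which is close to F × m when F is small.

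**Results**

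| Uncleared | Scored as failures | Half cleared outside | All cleared outside | Half opt out | All opt out |
|---|---|---|---|---|---|
| 10 | 90/100 = 90.0% (82.4–95.1) | 95/100 = 95.0% (88.7–98.4) | 100/100 = 100% | 90/95 = 94.7% | 90/90 = 100% (96.0–100) |
| 20 | 80/100 = 80.0% (70.8–87.3) | 90/100 = 90.0% (82.4–95.1) | 100/100 = 100% | 80/90 = 88.9% | 80/80 = 100% (95.5–100) |
| 30 | 70/100 = 70.0% (60.0–78.8) | 85/100 = 85.0% (76.5–91.4) | 100/100 = 100% | 70/85 = 82.4% | 70/70 = 100% (94.9–100) |

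With 10 uncleared and half cleared outside, the 5-point shift is about the distance from 90% to its upper limit (95.1 − 90.0 = 5.1 points). Smaller shifts lie within sampling error.

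**When status at the limit is known.** Five sessions span four intervals, so the fifth falls between week 4 × 8 = 32 and week 4 × 12 = 48. Its follow-up EGD, 8 to 12 weeks later, falls between week 40 and week 60. At 12-week spacing it falls at week 56 to 60, after month 12 counted from baseline. A rule tied to month 12 would therefore misjudge some patients.

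**The case against.** **No text says outside clearance counts.** A reader might infer that clearance by non-study ablation is scored as CE by the study device. The documents do not say so. They never mention non-study ablation of a trial patient after the limit; the clinical program is background experience, and the other techniques are named only to compare treatment schedules. What stands is that nothing excludes it.

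**Uncleared patients may not stay in.** A reader might infer from 3.7 that they remain to month 60. The opt-out is open to any subject, so this is not assured. But leaving does not cure the problem, because 7.4 then drops the failure from the denominator.

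**Failures are seen at month 12.** Table 2 labels only the 12-month EGD as the endpoint assessment, and a later rise would show beside that figure. This has weight for the month-12 result. However, 3.5.5 sends months 24 to 60 to the endpoint analyses as well, and the plan does not restrict durability to patients who cleared.

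**Few may be affected.** The preferred time is 10 seconds per site (3.5.2 step 9), and the earlier trial reported full regeneration in all 10-second areas. That bears on likely size, though 18 of 18 areas has an exact 95% interval of 81.5–100%, and areas are not patients.

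**It is a feasibility study.** Section 7.0 declares no hypothesis. CE is still a primary endpoint, and 7.2 still promises a comparison with historical data.

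**Conclusion.** The concern holds as a gap in the scoring rules. The plan does not say how patients uncleared at the limit are scored at months 24 to 60. Applied as written, 7.2 and 7.4 allow two routes by which a failure of the study regimen could read as a success or vanish. Compared with scoring these patients as failures, and holding all other patients fixed, both routes push CE upward only.

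The size cannot be derived from the documents. It depends on the share uncleared at the limit and the share of those later cleared outside the study or missing, and neither is given. The table is an illustration. The shift is zero if nobody is uncleared, or if nobody uncleared is treated outside or lost.

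A reader might be tempted to take a failure share from the 90% goal in 3.2 or from the 18% of 8-second areas without full regeneration in the earlier trial. Neither supports one. The goal is not stated as a share of patients and is not a forecast. The 18% is per area, in a trial of one or two ablations per subject, against up to five sessions here.

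The change is worth making because it is cheap and protects the long-term result.

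**What to change.** Add to 7.2, separately for CE of dysplasia and CE of BE:

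> A patient who has not reached that endpoint by the follow-up EGD after the last study cryoablation session (even if this EGD falls after month 12) is scored as not CE for that endpoint at all later time points and stays in the denominator, whatever non-study treatment is given and whether or not the patient opts out. CE as observed, regardless of non-study treatment, is shown as a second line. Durability is reported among patients who reached CE, with recurrence and retreatment reported separately.

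Keeping the endpoints separate means that a patient whose dysplasia cleared but whose BE did not is a failure only for BE. The durability sentence keeps retreated recurrences apart from patients who never cleared.

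Record any non-study ablation, resection or surgery, with its date, on the CRF at Stage 5 and 6 visits.

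**Cost.** A few sentences and one CRF item, with no extra patients, visits or procedures. It changes scoring only, not care. Long-term CE may be slightly lower. Part of that could be artefact if 7.4 still drops patients who cleared and then opted out: with 10 failures kept and 20 of 90 cleared patients missing, CE is 70/80 = 87.5% rather than 90%. The number of cleared patients missing should therefore be shown at each time point.
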